Bariatric surgery is rapidly gaining approval as a treatment for severe obesity, especially when complicated by DM2. An estimated 350,000 operations per year were performed globally at a cost of over \$5 billion (12). In centers of excellence, post-operative care is usually administered by the patient's endocrinologist and multi-disciplinary obesity teams and involves long-term evaluation of co-morbidity status, weight regain and multiple nutritional deficiencies. In the private sector, particularly, patients who are self-funding for surgery often do not choose to stay in follow up and high attrition rates remain a major challenge. Many observational studies and their meta-analyses have documented diabetes remission to occur in 78% of patients with morbid obesity (6,13,14). Two recent randomized control trials (2,4) document the effectiveness of gastric bypass surgery over intensive medical therapy to induce diabetes remission in the 42% range in patients with moderate obesity (BMI 30-40 kg/m²). However, long-term observational studies document a disquieting trend that a growing number of patients (25-40%) with DM2 do not achieve "biochemical remission" of hyperglycemia defined as normal glycemic control (HbA1c < 6% or <42 mmol/mol) without the need for diabetic medications (15), or are unable to sustain

this effect long-term despite initial success with weight loss (6,7,16). This proposal will target individuals who achieve early metabolic benefit, but are not able to sustain these effects long-term.

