variations in pre-surgical weight loss, and, occasionally, surgical failure that are often associated with psychosocial stressors (21). Prevention of weight gain requires optimizing patient selection criteria, consideration of benefits of bypass vs. banding or SG procedures, and adherence to scheduled visits. Psychological factors such as uncontrolled depression, eating disorders and previous history of sexual abuse has also been linked to weight regain and inadequate weight loss and warrant evaluation and continuing treatment (22). Post-surgical adherence to scheduled visits and compliance is also a major factor related to success of weight loss maintenance (20). The factors associated with re-development of DM2 following gastric bypass are related to poor baseline beta cell function in patients characterized by advanced duration (i.e., insulin requiring) and severity of DM2 (i.e., hyperglycemia) in older aged individuals (7,14). The incidence of residual or worsening DM2 following RYGB in one small study of 42 DM2 subjects was noted to be 26% 3 years following surgery and was associated with a lower pre-operative body mass index (BMI) (23). Although much of the literature has focused on biochemical remission following bariatric surgery, little information about the effects of surgery on long-term diabetes complications exist. The importance of on-going and continuous surveillance for micro-vascular complications in post-surgical patients is also warranted and will be addressed to some extent in this study.

Diabetes Therapies for Recurrent Diabetes Following Bariatric Surgery

Non-remission of hyperglycemia is noted by $HbA1c \geq 6.5\%$ and necessitate the use of diet and exercise counseling followed by the use of anti-diabetic medications. Initial preoperative assessment of DM2 should include documentation of type 1, latent onset autoimmune diabetes (LADA), or DM2 given the increasing prevalence of obesity in all

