Comparisons of the primary endpoint, change in HbA1c levels from randomization, between canagliflozin and placebo groups will be performed using analysis of covariance models. Since the correlation between baseline levels of HbA1c and change in the measure at 6 months is not presently well known, power calculations are based on use of two-sample t-tests, which assume similarity of the two randomized groups on HbA1c at baseline. Enrollment of 36 patients is planned. Assuming use of a two-sided t-tests with a significance level of 0.05, and that variability in HbA1c change at 6 months is similar to that seen at 1 year in Cefalu et al. (2013) [SD=0.9%], there will be 80% power to detect mean differences of 1.0% in HbA1c change between groups with enrollment of 22 patients in the canagliflozin group and 11 in the placebo group. Power calculations were performed using SAS software (Version 9.4; Cary, NC). If we assume dropout of 10%, and enroll 24 patients in the canagliflozin group and 12 in the placebo group, this should allow for adequate power despite the expected loss to follow-up. Since analysis of covariance models will provide increased

power relative to t-tests in the presence of positive correlation (Borm et al, 2007), the effect size that can be detected is conservatively large.

Nutritional assessment for vitamin/mineral deficiency will be performed per clinical care guidelines(46) at the screening visit. Subjects will be asked to take nutritional supplements (i.e. vitamins and minerals) per current clinical guidelines for post-bariatric patients. Stable doses of supplements will be established for at least 2 weeks prior to randomization. Thirty-six subjects with recurrent diabetes that are naïve to hypoglycemic agents with HbA1c greater than or equal to 6.5% and less than 11% will be randomly assigned to a six month course of a) canagliflozin 100mg for 2 weeks titrated up to 300 mg daily (N = 24) vs. placebo (n= 12) at the randomization. Patients taking an anti-diabetic medication will be asked to washout for 8 weeks prior to the randomization visit. At randomization, biochemical assessment of glycemic parameters (fasting glucose, HbA1c), lipid panel, complete metabolic panel, uric acid, leptin, total and HMW adiponectin, C-reactive protein and urine for albumin/creatinine ratio will be performed. DXA scan will be performed for body fat composition.

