The primary analysis will be performed using a modified intent to treat analysis which includes all patients receiving at least one dose of the drug they were assigned. A secondary, per-protocol analysis may also be performed using those demonstrating compliance to their assigned treatment throughout the study. All endpoints will be evaluated using a significance level of 0.05, and no correction for multiple testing is planned.

To evaluate changes in HbA1c and other continuous endpoints at 6 months, analysis of covariance models will be fit. In these models, change from baseline will be the outcome, group membership will be the predictor of interest, and baseline level of the outcome will be a covariate. If distributional assumptions of the model are not met, transformation of the outcome measure will be considered to improve model fit, as will the use of alternative rank-based approaches. Estimated changes and differences in the changes at 6 months between groups will be presented with 95% confidence intervals. Categorical factors will be presented using frequencies and percentages, and comparisons of these measures between groups will be performed using Pearson chi-square tests or Fisher exact tests, as appropriate. Continuous patient characteristics will be summarized using means and standard deviations or medians and quartiles, depending on their distribution.

Inclusion Criteria:

1. Post-AB, RYGB, and SG patients who underwent surgery >1 and <15 years ago, in the Cleveland surrounding area
2. 20-75 years of age

3. DM2 diagnosis (history, medication usage, biochemical criteria) prior to and after surgery; after surgery, defined by a single HbA1c of greater or equal to 6.5% at consent and screening.

4. Metformin patients must have an HbA1c greater than or equal to 6.5% but less than or equal to 11% at randomization; for diet controlled patients (i.e. not on any T2D medication), HbA1c must be greater than or equal to 6.5% at randomization.

5. Patient reporting of improvement in T2D status or objective improvements in T2D status at any time post-surgery.

6. eGFR \geq 60mL/min prior to randomization

7. Has the ability and willingness to provide informed consent.

8. Is able to understand the options and to comply with the requirements of each program.

9. Female subject agrees to have a serum pregnancy test at screening. A negative serum pregnancy test result is required prior to randomization.

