Visit 3: Randomization visit with research coordinator and PI: Review of eligibility. Labs will be drawn for HbA1c, fasting glucose, lipid panel, uric acid, complete metabolic panel and adipokines (C-reactive protein, leptin, total and HMW adiponectin, leptin). Urine for albumin/creatinine ratio. DXA scan will be performed for body composition at this visit. Blood and urine will be collected for the bio-repository collection and is optional.

Visit 4: 6 week f/u visit: Research fellow/coordinator to assess adherence and safety.

Visit 5: 3 month visit with research coordinator and PI: Review of clinical status and biochemical labs will be drawn. These will include HbA1c and a complete metabolic panel.

Visit 6: 6 month visit with research coordinator and PI: Review of clinical status and biochemical labs will be drawn. These include HbA1c, fasting glucose, lipid panel, uric acid, complete metabolic panel and uric acid. Urine for albumin/creatinine ratio. Additionally, a DXA scan for body composition and blood for adipokines (C-reactive protein, total and HMW adiponectin, leptin) will be performed. Blood and urine will be collected for the bio-repository collection and is optional.

The window for all visits will be +/- 4 weeks.

Research Team: [name] is the principal investigator of this study and will consult with [name] (bariatric surgeon) for enrollment of appropriate candidates who underwent metabolic surgery at any Cleveland Clinic location, but that live within two hours of the Cleveland Clinic Main Campus. Both investigators have a long standing,

productive relationship. Statistical analysis will be provided by a Cleveland Clinic Quantitative Health Sciences statistician dedicated to endocrine and diabetes research. This team is well qualified to run post-bariatric trials and have successfully run two randomized control trial of bariatric vs. medical therapy for type 2 diabetes in obese patients.

POSSIBLE RISKS

Risks associated with Canagliflozin Include:

All drugs can cause unwanted effects called side effects. As of 28 September 2015 approximately 13173 subjects have received canagliflozin in completed or ongoing studies of 12 weeks or longer.

Side effects found in these studies that are more likely to occur with canagliflozin include those below. You should speak with your doctor about any changes to your diet or other medications you are taking:

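### The primary set is all dosed patients, but the 6-month ANCOVA leaves out the 3 to 4 expected dropouts and ignores the 3-month HbA1c already drawn (minor)

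*Combined protocol and SAP*

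**What the plan says.** All references are to the combined protocol and SAP.

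- **Analysis set** (Statistical Methods): the primary analysis is a "modified intent to treat analysis which includes all patients receiving at least one dose of the drug they were assigned".
- **Model** (Statistical Methods): "To evaluate changes in HbA1c and other continuous endpoints at 6 months, analysis of covariance models will be fit". The outcome is change from baseline, with terms for group and baseline level. Transformation or rank-based methods are the fallback if model assumptions fail.
- **Dropout** (Sample Size Considerations): "If we assume dropout of 10%, and enroll 24 patients in the canagliflozin group and 12 in the placebo group". The calculation needs 22 and 11, so dropout is handled by enrolling more patients.
- **ANCOVA gain** (same section): ANCOVA is expected to add "power relative to t-tests in the presence of positive correlation".
- **3-month HbA1c** (Schedule of visits, Visit 5): biochemical labs are drawn. "These will include HbA1c and a complete metabolic panel". No described analysis uses this value.
- **Visit windows** (same section): "The window for all visits will be +/- 4 weeks".

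There is no imputation rule, mixed model or missing-data sensitivity analysis.

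**The concern.** A dosed patient without a 6-month HbA1c belongs to the stated primary set but has no outcome in the stated model. The set described and the set analysed therefore differ, and the plan expects this to happen. Enrolling extra patients protects power. It does not address whether those who remain represent those who were randomized.

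A 6-month complete-case ANCOVA is unbiased when dropout is unrelated to the 6-month response, given arm and baseline. A likelihood analysis that includes the 3-month value needs less: dropout may also depend on the observed 3-month HbA1c. The data for that weaker assumption are already collected. At stake are a little precision in all cases with dropout after month 3, and some protection against attenuation if dropout follows early response.

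**Working it through.** **1. The plan's own figure.** Inputs from Sample Size Considerations: two-sided alpha 0.05, SD 0.9, difference 1.0, 22 against 11.

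- SE = 0.9 × √(1/22 + 1/11) = 0.332; noncentrality = 1.0/0.332 = 3.01; df = 31.
- Noncentral-t power = 83.0%. The stated 80% is met (20 against 10 gives 79.1%).

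**2. Patients who fall out.** 24 × 0.9 + 12 × 0.9 = 21.6 + 10.8 = 32.4, so 36 − 32.4 = 3.6 patients.

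**3. Expected gain under random dropout.** Let m be the fraction with only a 3-month value and ρ the 3-to-6-month correlation of change. In large samples the variance of the repeated-measures estimate relative to ANCOVA is 1 − mρ². With m = 0.1:

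- ρ = 0.5: 1 − 0.1 × 0.25 = 0.975
- ρ = 0.7: 1 − 0.1 × 0.49 = 0.951
- ρ = 0.85: 1 − 0.1 × 0.7225 = 0.928

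Simulation at 24 against 12 gives 0.974, 0.946 and 0.919.

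**4. Simulation of both models.** From the plan: 24/12, SD 0.9, difference 1.0, 10% dropout. Assumed, because the documents give no figures:

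- 3-month difference 0.85
- placebo drift +0.15 at 3 months and +0.3 at 6 months
- baseline mean 8, SD 1.1, truncated to 6.5–11
- ρ as shown
- all dropout after month 3, with log-odds linear in the 3-month change

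The repeated-measures model uses REML, unstructured covariance and Kenward-Roger. There were 8,000 to 16,000 trials per setting. The odds multiplier is exp(slope) per 1% HbA1c.

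| Dropout | ρ | ANCOVA: estimate, power | Repeated measures: estimate, power |
|---|---|---|---|
| Random | 0.5 | 1.00, 80% | 1.00, 82% |
| Random | 0.7 | 1.00, 81% | 1.00, 82% |
| Random | 0.85 | 1.00, 81% | 1.00, 84% |
| Slope 0.25 (odds ×1.28) | 0.7 | 1.00, 81% | about 1.00 |
| Slope 0.5 (×1.65) | 0.7 | 0.995, 80% | about 1.00 |
| Slope 1.0 (×2.7) | 0.7 | 0.963, 78% | 1.000, 82% |
| Slope 1.5 (×4.5) | 0.7 | 0.934, 75% | 0.999, 82% |
| Slope 2.0 (×7.4) | 0.7 | 0.909, 74% | 0.999, 82% |
| Slope 1.5 | 0.5 | 0.953, 76% | 0.999, 80% |
| Slope 1.5 | 0.85 | 0.919, 75% | 0.998, 84% |

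Slopes of 1 to 2 correspond to losing about 15–18% of placebo and 6–8% of canagliflozin patients. A separate simulation (3-month difference 0.8, ρ 0.5–0.9, slopes 1 and 2) gave 0.89–0.97 for complete-case ANCOVA and about 1.00 for the likelihood analysis.

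**5. Limits.**

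- All dropout before month 3: the two models are identical.
- Half early and random, half by 3-month response: ANCOVA lies between 0.96 and 1.00, depending on slope.
- Dropout driven by the unobserved 6-month level: both are attenuated, 0.89 for ANCOVA and 0.94 for repeated measures.
- Type I error with no true difference: 0.051–0.052 for ANCOVA, 0.049–0.050 for repeated measures.

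**6. Feasibility.** Three and six months are about weeks 13 and 26. With ±4 weeks the windows are weeks 9–17 and 22–30. They do not overlap, so visit can be categorical. The model converged in all 16,000 trials of each main 10% setting.

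**The case against.** The strongest objection is that a prespecified ANCOVA is a standard primary analysis and that little is lost by keeping it. Much of this stands. The attenuation needs strong dependence, and at odds multipliers up to 1.65 it is barely detectable. Even in the strong cases the shift of 0.04–0.09 is small beside a sampling SD of about 0.34, mean squared error improves by only about 5%, and the error is toward the null.

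A reader might infer that the plan will understate the drug effect, because poor responders on placebo will leave. The documents do not support this. The Background remark that "high attrition rates remain a major challenge" concerns the private sector, particularly patients paying for their own surgery; this is a funded trial at one clinic. The section on re-emergence of diabetes says "Post-surgical adherence to scheduled visits and compliance is also a major factor related to success of weight loss maintenance". That links attendance to weight maintenance; it does not say that a poor HbA1c response causes dropout. Other text weakens or reverses the inference. Rescue is available in both arms, which reduces the motive to leave for poor glucose control. Possible Risks describes dizziness and allergic reactions soon after starting canagliflozin, and dropout from these would be early and in the active arm.

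A reader might also infer that the trial is underpowered. It is not: 22 against 11 gives 83.0%. If the ANCOVA gain is credited, with an assumed baseline-to-change correlation of 0.3 or 0.5, ANCOVA keeps 80% or 87% power even at slope 1.5 (repeated measures 86% or 92%).

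What the objection does not remove is the mismatch between the set and the model, or the unused measurement. In the settings compared, the repeated-measures model had no higher mean squared error than ANCOVA.

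**Conclusion.** The gap is real and minor. About 3.6 of 36 dosed patients are expected to fall out of an analysis described as including them, and a measurement that would keep some of them in is not used. That part follows from the text alone.

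The size of the benefit rests on assumptions. With dropout after month 3 it is about 2–8% lower variance if dropout is random, and recovery of 0.04–0.09 of a 1.0 difference if dropout depends strongly on 3-month response. If patients leave before month 3 there is no benefit. The documents do not show which pattern will occur, so this is a cheap improvement and not evidence that the planned result would be biased.

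**What to change.** 1. Make the primary HbA1c analysis a likelihood-based repeated-measures model of change at 3 and 6 months, with arm, visit, arm-by-visit and baseline-by-visit terms, unstructured covariance and Kenward-Roger degrees of freedom. Keep the primary contrast at 6 months.
2. Keep the planned ANCOVA, with its transformation and rank-based fallbacks, as a sensitivity analysis.
3. Report by arm how many dosed patients have no post-baseline HbA1c and how many have only the 3-month value.
4. Fix this wording before unblinding. Limit it to HbA1c, because lipids, DXA and adipokines have no 3-month measurement.

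**Cost:** slightly more analysis work, and no new visits, samples or patients. The model assumes data are missing at random given arm, baseline and 3-month HbA1c, and it does not recover patients lost before month 3.

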Following randomization, subjects will be clinically evaluated at three office visits at 6 weeks, 3 and 6 months by PI and/or the research staff. The primary outcome measures at 6 months post-randomization include HbA1c followed by the change in HbA1c from randomization. Secondary measures include fasting glucose, BMI, change in body weight, blood pressure, lipid profile. Symptomatic hypoglycemia (blood glucose < 70) and drug related side effects (i.e. mycotic genital infections, urinary tract infection) will be monitored with adverse event reporting. Metabolic testing in all subjects at randomization and at 6

months will include a DXA scan for body fat composition and blood for leptin and adiponectin levels.

Rescue glucose lowering therapy will be provided for all subjects with a blood glucose >250 mg/dl. If chronic uncontrolled hyperglycemia (HbA1c $>11\%$) occurs then basal bolus insulin will be implemented. Subjects (20-75 years) who underwent AB, SG or RYGB within the past 15-years will be recruited. Including subjects who underwent surgery within the past 15-years will broaden the subject pool, as additional subjects who initially remitted and were subsequently rediagnosed will be identified. However, we will prioritize subjects who underwent metabolic surgery ≤ 6 years ago and who initially achieved remission status documented by HbA1c of $\leq 6.5\%$ within first year and a subsequent glycated hemoglobin $\geq 7.5\%$ (without any hypoglycemic agents) and less than 11% as upper limit. The rationale to prioritize patients that initially remit is that these patients have demonstrated ability to respond to surgical weight loss and subsequently redeveloped the disease. Whereas those that never achieved initial remission status may not respond to any intervention due to inexorable beta cell failure.

Initial recruitment will be achieved by a general awareness campaign, which will emphasize a study of methods of diabetes management post metabolic surgery. All patients will be pre-screened for inclusion and exclusion criteria by our clinical trial research nurse coordinator and/or research fellow. Evaluation of the inclusion and exclusion criteria, which are listed below, will occur both at the initial screening visit and the baseline visit, prior to randomization.

Statistical Methods

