10. Female patients must agree to use a reliable method of contraception for 6 months

or

duration of intervention.

11. Excluding research-related insulin use, patients taking an anti-diabetic medication, except insulin, are eligible and must

agree to washout for 8 weeks prior to the randomization visit.

Exclusion Criteria:

1. Type 1 diabetes indicated by history of diabetic ketoacidosis and lack of remission in response to bariatric surgery.

2. Other post bariatric procedures (banding, duodenal switch, biliopancreatic diversion)
3. Non-research-related insulin use that is prescribed by the patient's primary care physician or endocrinologist
4. End organ diabetic complications (renal failure, cardiomyopathy, severe neuropathy/foot ulcers)
5. Documented severe or unstable depression/anxiety or eating disorder that would not enable patient to adhere to anti-diabetic treatment.
6. Clinical contraindications to use canagliflozin, i.e., history of bladder cancer, Child-Pugh class C.

In addition to a urine sample, a maximum of 60-cc of blood may be needed at each visit; 30-cc will be stored as a biorepository, for future purposes. The biorepository will be performed at randomization and at the 6 month visit. The research repository collection will be part of the protocol. The identity of the subject will be confidential as the samples will be deidentified. Specimens will be processed and stored in Preventive Research Laboratory at Cleveland Clinic. Access to these specimens will be limited to the designated PRL laboratory personnel and utilized at the discretion of the Principal Investigator.

Schedule of visits summarized:

Visit 1: Consent and Screening Visit: An assessment of clinical status for eligibility will be performed. Review of past medical history and medication usage will be reviewed. Venipuncture for HbA1c and a pregnancy test (females only). Labs for nutritional status

including B12 and 25 hydroxy vitamin D will be performed. Nutritional deficiencies will be addressed per current clinical guidelines for post-bariatric patients.

Visit 2: Baseline Visit: 45 minute visit with diabetes educator for diet/exercise prescription and glucose monitoring based on ADA clinical care guidelines.

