An adverse event is considered unlisted if the nature or severity is not consistent with the applicable product reference safety information. For a medicinal product(s) with a

marketing authorization, the expectedness of an adverse event will be determined by whether or not it is listed in the applicable product information.

III. Special Situations

Safety events of interest for a Janssen medicinal product that require expediting reporting and/or safety evaluation include, but are not limited to:

- Drug exposure during pregnancy (maternal and paternal)
- Overdose of a Janssen medicinal product
- Exposure to a Janssen medicinal product from breastfeeding
- Suspected abuse/misuse of a Janssen medicinal product
- Inadvertent or accidental exposure to a Janssen medicinal product
- Any failure of expected pharmacological action (i.e., lack of effect) of a Janssen medicinal product
- Medication error involving a Janssen medicinal product (with or without patient exposure to the Janssen medicinal product, e.g., name confusion)
- Suspected transmission of any infectious agent via a medicinal
- Unexpected therapeutic or clinical benefit from use of a Janssen medicinal product

These safety events may not meet the definition of an adverse event; however, they are treated in the same manner as adverse events. Special situations should be recorded on the Adverse Event page of the CRF.

Any special situation that meets the criteria of a serious adverse event should be recorded on a Serious Adverse Event Report Form and be reported to Janssen Scientific Affairs **within 24 hours of becoming aware of the event.**

IV. Management of Hyperglycemic Events

A sliding scale will be implemented for the management of hyperglycemia in the placebo or canagliflozin treated groups and during the anti-diabetic medication washout

period if a subject develops random blood sugars >250 mg/dl. Subjects will use the following sliding scale:

Sliding scale with human regular insulin:

0-250: 0 units

251-300- 6 units

301-350- 8 units

351-400- 10 units.

If chronic uncontrolled hyperglycemia occurs (HbA1c > 11%) in the placebo or canagliflozin treated group then basal bolus insulin will be implemented. Basal bolus insulin will be initiated based on body weight calculation 0.5 U/kg/day with 50% of the dose given with long-acting insulins (NPH, glargine) and the remaining dose with meal insulin with rapid acting insulin (Regular, Humalog, Novolog, Apridra etc.).

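### Inclusion item 4 caps HbA1c only for metformin patients, so the listed criteria admit patients above both the stated 11% limit and the insulin rescue threshold

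*Combined protocol and SAP*

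**What the plan says.** The combined protocol and SAP gives the HbA1c entry range in more than one place.

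- **Design text under Sample Size Considerations.** The thirty-six subjects are described as naïve to "hypoglycemic agents with HbA1c greater than or equal to 6.5% and less than 11% will be randomly assigned". This is one range for everyone randomised.
- **Inclusion Criteria, item 4.** "Metformin patients must have an HbA1c greater than or equal to 6.5% but less than or equal to 11% at randomization"; then "for diet controlled patients (i.e. not on any T2D medication), HbA1c must be greater than or equal to 6.5% at randomization". The first clause has a floor and a ceiling, the second only a floor.
- **Inclusion Criteria, item 3.** A floor of 6.5% at consent and screening, with no ceiling.
- **Inclusion Criteria, item 11.** "patients taking an anti-diabetic medication, except insulin, are eligible and must" agree to an 8-week washout. No HbA1c limit is given.
- **Exclusion Criteria.** None of the six items mentions HbA1c.

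On how eligibility is judged, the text just before Statistical Methods says: "Evaluation of the inclusion and exclusion criteria, which are listed below, will occur both at the initial screening visit and the baseline visit".

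On rescue, Management of Hyperglycemic Events says: "If chronic uncontrolled hyperglycemia occurs (HbA1c > 11%) in the placebo or canagliflozin treated group then basal bolus insulin will be implemented". The same threshold appears in the design text. A sliding scale of regular insulin applies when blood glucose exceeds 250 mg/dl.

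**The concern.** The two entry rules give different answers for the same patient, and the more permissive one is in the list that staff are told to use. The patient it lets in is one whom the protocol would itself describe as having chronic uncontrolled hyperglycaemia.

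Two things are at stake. The first is safety: a patient above the protocol's own basal-bolus threshold could be allocated to six months of placebo. The second is interpretation: if that patient is put on basal-bolus insulin at or near entry, the HbA1c change at 6 months no longer reflects canagliflozin monotherapy against placebo. Statistical Methods analyses everyone who took at least one dose and gives no rule for HbA1c values recorded after rescue insulin. No loss of power is claimed.

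**Working it through.** **Sample size.** The plan's figure does not depend on this point, and it reproduces. With a two-sided 0.05 t-test, a difference of 1.0%, SD 0.9% and 2:1 allocation, the noncentral t gives 83.0% power at 22 + 11 and 79.1% at 20 + 10. So 22 + 11 is the smallest 2:1 size with at least 80% power.

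**The entry rules side by side**

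| Patient at randomisation | Design text | Listed criteria |
|---|---|---|
| Metformin, HbA1c 11.5% | barred | barred (item 4) |
| Metformin, exactly 11.0% | barred (must be below 11%) | allowed (up to and including 11%) |
| Diet-controlled, 11.5% | barred | allowed (item 4, floor only) |
| Washed out of another non-insulin drug, 11.5% | barred | no ceiling in items 3, 4 or 11 |

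The third row is the main problem, and 11.5% is above the basal-bolus threshold of more than 11%. The fourth row holds whether or not these patients are read into the diet-controlled clause.

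**What happens to such a patient.** Placebo is 12 of 36, a chance of 1/3. The rescue wording can be read in two ways:

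- *The trigger applies at entry.* Basal-bolus insulin starts at 0.5 U/kg/day at or near baseline, and the monotherapy comparison is lost for that patient. One patient is 1/12 = 8% of the placebo arm.
- *The trigger applies only to hyperglycaemia arising on treatment.* The next scheduled HbA1c is at the 3-month visit, where labs are drawn and "These will include HbA1c and a complete metabolic panel". Since "The window for all visits will be +/- 4 weeks", that visit can fall at about 13 + 4 = 17 weeks. Until then the sliding scale is the only written rescue.

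**How many patients.** The documents give no HbA1c distribution for the screened population. As an assumption, take the two pre-treatment values in Preliminary Data, item 5 (8.4 ± 1.3 and 8.1 ± 1.4) as means and SDs of normal distributions.

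- Upper tail: z = (11 − 8.4)/1.3 = 2.00, p = 0.0228; z = (11 − 8.1)/1.4 = 2.07, p = 0.0192.
- Among those at or above 6.5%: 0.0245 and 0.0219.

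| | Mean 8.4, SD 1.3 | Mean 8.1, SD 1.4 |
|---|---|---|
| Expected in 36 (36p) | 0.82 | 0.69 |
| Same, given ≥6.5% | 0.88 | 0.79 |
| Expected in 12 on placebo (12p) | 0.27 | 0.23 |
| Same, given ≥6.5% | 0.29 | 0.26 |
| At least one in 36, 1 − (1 − p)^36 | 0.563 | 0.502 |
| Same, given ≥6.5% | 0.591 | 0.550 |

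These rows treat all 36 as uncapped, so they are upper values under this model. If only 18 are uncapped, the expected number given ≥6.5% is 0.44 or 0.39, and the chance of at least one, 1 − (1 − p)^18, is about 36% or 33%.

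**The case against.** The strongest reply is that item 4 is silent rather than contradictory. It does not say that values above 11% are acceptable, and both texts can be satisfied by applying the limit of less than 11% to everyone. That is logically true, but it does not help whoever applies the criteria. Eligibility is referred to the list, nothing says the design text overrides it, and the eligibility review at the randomisation visit names no separate limit. Nor does the omission look deliberate. The design text attaches its ceiling to drug-naïve subjects, and the ceiling for prioritised subjects also applies to people on no glucose-lowering drug. These are the patients whom item 4 leaves uncapped.

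Second, there are safeguards: the diabetes educator covers glucose monitoring, a 6-week visit assesses adherence and safety, and the sliding scale is active rescue that does not wait for an HbA1c result. These reduce the risk. However, the 6-week visit lists no HbA1c, and none of them keeps the patient out.

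Third, rescue insulin can confound the comparison in either arm whatever the entry HbA1c, and baseline HbA1c is a covariate. Both points are fair. But adjusting for baseline does not remove the effect of insulin given afterwards, and the gap adds a patient who may need insulin from the first day.

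Fourth, the counts are soft. Nothing shows that diet-controlled patients here resemble those in the preliminary data, and some of the 36 will be capped metformin patients. This stands, and the counts should carry little weight.

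Last, a limit of 11% or below for everyone would also keep out patients above the rescue threshold. That is correct; the reason to prefer below 11% is that the design text already states it.

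**Conclusion.** The concern holds. As listed, the inclusion criteria admit a patient whom the design text bars and who already exceeds the protocol's threshold for basal-bolus insulin. This follows from the text alone and needs no assumption.

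The number affected is unknown and probably small: about 2% of patients, or 0.7 to 0.9 expected among 36 with 0.2 to 0.3 on placebo, and about 0.4 in total if half are uncapped. Those figures rest on normality, on the similarity of the preliminary-data patients to those screened here and, except for the last, on all 36 falling under the uncapped rule. The issue is an ambiguous entry rule with a safety consequence for an individual and possible confounding of the primary comparison. It should be fixed, but it does not threaten the design.

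**What to change.** Replace inclusion item 4 with a single range for every participant, whatever the prior treatment: HbA1c of at least 6.5% and below 11% at randomisation. This brings the list into line with the design text, covers patients washed out of drugs other than metformin, and removes the mismatch at exactly 11.0%. Nobody is then randomised above the rescue threshold.

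The cost is one amended criterion. About 2% of screened patients become ineligible under the assumption above, and a metformin patient at exactly 11.0% is newly excluded. Sample size, endpoint and analysis stay as they are.
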